## 7. LOCAL ADVERSE EVENTS

Any local adverse event (LAE) occurring during the tested treatment, irrespective of its severity, must be recorded in the case report form, in the pages provided for this purpose.

The onset of an adverse event may lead to a withdrawal of the study treatment, either temporarily or definitively.

### **The following will be recorded:**

- The nature and date of onset,
- The causal relationship with current treatment,
- The outcome,
- The therapeutic decision.

### **The occurrence of a local adverse event**

- Does not necessarily represent a reason for premature study withdrawal,
- Leaves the investigator free to continue or to stop the study treatment, either temporarily or definitively, in this case replacing it with a treatment considered to be more appropriate, based on his/her clinician experience,
- Must be documented in the case report form and will be the subject of a clinical, and photographic assessment.

If an adverse event requires the investigator to discontinue definitively the study treatment, this must be documented in the Case Report Form, on the “Early termination before W12”.

Any local adverse event involving the permanent discontinuation of treatment must be reported by the patient and/or the community HCP, to the principal investigator by phone within 48 hours and by email within 3 days.

If the occurrence of a local adverse event leads to a temporary discontinuation of the study treatment, this should not exceed 2 weeks; after that it becomes permanent and the investigator will then have to complete the “Early termination before Week 12” section in the Case Report Form.

The investigator could then document the description of this adverse event and its evolution in a specific materiovigilance document and send it to the manufacturer of the two tested devices ([[contact]](mailto:[contact])).

## 8. INTERCURRENT ADVERSE EVENTS

Any untoward intercurrent medical occurrence in a patient or clinical investigation subject administered an investigational product and which does not necessarily have a causal relationship

with this treatment will be considered as an Intercurrent Adverse Event. An intercurrent adverse event (IAE) can therefore be any unfavourable and unintended sign (including an abnormal laboratory finding, for example), symptom, or disease temporarily associated with the use of an investigational product, whether or not considered related to the tested procedure.

Any intercurrent adverse event occurring during the treatment will be recorded in the Case Report Form, in the pages provided for this purpose.

## **9. SERIOUS ADVERSE EVENTS**

Any Serious Adverse Event (SAE) is any untoward medical occurrence that:

- Results in death,
- Is life-threatening,
- Requires inpatient hospitalization or prolongation of existing hospitalization,
- Results in persistent or significant disability/incapacity,
- Corresponds to another important medical event,

will be reported by the patient and/or the community HCP to the principal investigator by telephone within 48 hours.

The investigator must inform the local ethics committee in accordance with the local regulations and guidelines and should inform the manufacturer (Laboratoires Uργο Medical) at the following email address: [[contact]](mailto:[contact]).

## **10. STATISTICAL ANALYSIS**

### **10.1. NUMBER OF SUBJECTS**

Given the uncontrolled nature of this clinical study, the data available in the literature in this area, and the treatment duration of twelve weeks for each patient, it appears that the total number of 60 patients is sufficient to provide a relevant answer to the primary endpoint. This has been agreed with our medical statistician who is independent of this study.

No statistical tests will be applied because this clinical study is non-comparative.

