## INTRODUCTION

Chronic venous insufficiency (CVI) of the lower limbs is a common condition affecting 5–30% of the adult population worldwide, with a prevalence that is consistently increasing with age (1-5).

The ultimate stage of CVI (the C6 stage) according to the CEAP classification (clinical, etiological, anatomical and pathophysiological) is represented by the venous leg ulcer (VLU), which can often take several months or even years to heal; only 30–75% of patients seem to achieve wound closure after six months of treatment, depending on the severity of the ulcer and the patients' health status (6,7).

According to guidelines, and based on systematic reviews, the management of these wounds requires a holistic approach, combining suitable local wound care with an adapted aetiological treatment based on an effective and high compression therapy applying 40 mmHg at the ankle in the acute decongestion phase of oedema and for the treatment of an active VLU (8).

Very positive clinical outcomes provided by a randomized controlled trial involving 187 patients comparing a four-layer bandage with a two-layer bandage compression system UrgoK2 (9) as well as a very large clinical evaluation including 702 patients treated under real-life conditions, have confirmed the efficacy and safety profile of this multicomponent compression system (10). Both of these clinical evaluations have supported the efficacy of this high compression therapy in healing VLUs, reducing lower limb oedema caused by CVI and improving the Quality of Life of patients. The real-life study even brought growing evidence supporting the use of this compression system, as a first-line intervention (higher healing rate when used in first intention) in the treatment of VLUs.

Venous leg ulcers are characterized by elevated and prolonged expressions of matrix metalloproteinases (MMPs) in the wound tissue and fluid which have been correlated to the impaired healing and chronicity and mixed arterial ulcers also have an impaired perfusion (11). Addressing this protease imbalance by reducing the high levels of MMPs could represent a possible therapeutic modality to improve ulcer healing (12-13).

Wound dressings including the Technology Lipido-Colloid with Nano Oligo Saccharide Factor (TLC-NOSF) are known for their protease inhibiting properties and positive impact on chronic wound healing; their efficacy and acceptability for patients and caregivers, when associated with good

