## 6. ASSESSMENT CRITERIA

### 6.1. MAIN CRITERION

The main judgment criterion is the completely closed study ulcer (100% re-epithelialization) evaluated at last available study visit (12 weeks, at the latest).

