### **10.3. GENERAL STATISTICAL CONSIDERATION ON DESCRIPTION OF VARIABLES**

The distribution of parameters will be summarized using descriptive statistics according to characteristics of the study variable:

- Binary, nominal and ordered categorical variables will be summarized by their frequency distribution,
- Continuous variables will be summarized by their number of observations, mean, standard deviation, median, quartiles and range.

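### Does the protocol need to state the precision that 60 patients give before it can call that number sufficient?

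*Protocol*

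**What the plan says.** The study is open, has a single arm, runs at one centre and plans to include 60 patients (protocol section 1). The main criterion is complete closure of the study ulcer, judged at the last available visit and no later than week 12 (section 6.1).

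Section 10.1 bases the number on general grounds: "Given the uncontrolled nature of this clinical study, the data available in the literature in this area, and the treatment duration of twelve weeks". From these it concludes that "it appears that the total number of 60 patients is sufficient to provide a relevant answer to the primary endpoint", and adds: "This has been agreed with our medical statistician who is independent of this study". It closes with: "No statistical tests will be applied because this clinical study is non-comparative".

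Section 10.3, which sets generic summaries by type of variable, states: "Binary, nominal and ordered categorical variables will be summarized by their frequency distribution". The protocol shown mentions no confidence interval for the closure proportion. Section 10.2.1 carries the heading of a statistical analysis plan but says only who will analyse the data and when. A separate SAP may exist; it was not available for this review.

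**The concern.** Three features of section 10.1 look weak when read together.

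- **Sufficiency without a yardstick.** A number can be called sufficient only against a stated aim, such as an interval width or a rate to be excluded. None is given. The appeal to "the data available in the literature in this area" carries no figure. The only closure rate in the text is in the Introduction, "only 30–75% of patients seem to achieve wound closure after six months of treatment". That is a six-month range, whereas the endpoint is read at 12 weeks at the latest and the ulcers must be under six weeks old (section 4.2). The range is not linked to the number 60.
- **A reason that proves less than it claims.** Having no comparator rules out tests between groups. It does not rule out a one-sample test or an interval.
- **A bare percentage.** If closure were reported only as a frequency, a reader would not be told how far the true proportion might lie from it, in a study whose stated objective is to assess efficacy.

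At stake would be over-reading of the primary percentage, and possibly a study too small for its purpose.

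**Working it through.** **Can 60 be reproduced?** No. Any sample-size formula for one proportion needs an expected or reference rate together with a precision target, or with an error rate and power. Section 10.1 gives none of these. The useful check is therefore what 60 delivers.

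**Inputs.** n = 60 (sections 1 and 10.1); a binary endpoint (section 6.1). Assumptions: a two-sided 95% level, since the protocol states none, and closure ranged over 30% to 75%. That range is borrowed from the Introduction for illustration only, because it refers to six months.

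**Simple approximation.** Half-width = 1.96 × √(p(1 − p)/n).

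- p = 0.30: 1.96 × √(0.21/60) = 11.6 points
- p = 0.50: 1.96 × √(0.25/60) = 12.7 points (the maximum)
- p = 0.75: 1.96 × √(0.1875/60) = 11.0 points

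Inverting it, n = 1.96² × p(1 − p)/h². At p = 0.50, a half-width h of 10 points needs 97 patients, 12.5 points needs 62, 13 points needs 57 and 15 points needs 43. So 60 corresponds to a worst case of about 12.7 points on this approximation.

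**Exact (Clopper-Pearson) interval.** For x closures, the lower limit is the 2.5% quantile of Beta(x, n − x + 1) and the upper limit is the 97.5% quantile of Beta(x + 1, n − x).

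| Closed / 60 | Estimate | Exact 95% interval | Distance to farther limit |
|---|---|---|---|
| 18 | 30% | 18.8 to 43.2% | 13.2 points |
| 24 | 40% | 27.6 to 53.5% | 13.5 points |
| 30 | 50% | 36.8 to 63.2% | 13.2 points |
| 36 | 60% | 46.5 to 72.4% | 13.5 points |
| 45 | 75% | 62.1 to 85.3% | 12.9 points |

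Over all x from 0 to 60 the largest distance is 13.46 points, reached at 24/60 and 36/60. For any result from 18 to 45 closures, the farther limit lies 12.9 to 13.5 points away. At other levels the maximum is 11.4 points (90%) and 17.4 points (99%).

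**Smaller denominator.** The ITT population in section 10.3.1 requires at least one documented ulcer status after inclusion, so fewer than 60 patients may be analysed. The protocol states no loss rate. Assumed losses of 5%, 10% and 20% leave 57, 54 and 48 patients, and the exact 95% maximum becomes 13.8, 14.2 and 15.1 points. The figure for 60 is thus the best case.

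**Is the reason for having no tests too strong?** As logic, yes. With an assumed reference rate of 50% and an assumed true rate of 70%, a rule requiring at least 39 of 60 ulcers closed has an exact one-sided error rate of 0.014 and power of 0.838. A one-sample test is therefore possible without a comparator. But both rates are invented for the illustration. The protocol names no reference rate, so there is nothing for such a test to be run against.

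**Would following the plan as written give a different result?** No. The estimate is the number closed divided by the number analysed, whether or not section 10.1 states a precision. An analyst can put an exact interval beside it from that count and denominator alone.

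**The case for a change.** The strongest case for a change is that the sample-size rationale belongs in the protocol. Section 10.1 sets out to give one, so a later SAP cannot repair it. The statistician's agreement records that the number was accepted but not what it delivers. A reader told only that 60 is sufficient would not learn that an observed 50% is compatible with roughly 37% to 63%. The remedy would be cheap: two sentences and one interval.

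Part of this stands. Section 10.1 asserts sufficiency without saying what it means, and its reason for having no tests is looser than it should be. Neither point reaches as far as a required change.

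- The wording in section 10.1 is hedged and claims no power. The decision to run no tests is sound for a descriptive single-arm study, whatever reason is given for it.
- The primary interval, with its method and level, is what a protocol commonly leaves to the SAP. Section 10.3 sets generic summaries and forbids nothing further.
- The obvious replacement sentence, promising limits no more than about 13.5 points away, would itself need the condition that all 60 patients are evaluable.

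**Conclusion.** The observation is accurate but calls for no change to the plan. Section 10.1 omits a precision statement; it does not fix a wrong number, a wrong endpoint or a wrong analysis. No stopping rule, success criterion or comparison depends on the interval width, no extra enrolment is implied, and the closure proportion would be the same either way. What is missing is detail that an analyst supplies as a matter of routine.

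On size: assuming an exact two-sided 95% interval, the limits lie at most 13.5 points from the estimate with 60 evaluable patients, and at most 15.1 points with 48 (an assumed 20% loss). The confidence level and the loss rates are assumptions, since the protocol states neither. If the sponsor amends section 10.1 for other reasons, stating these figures in place of the sufficiency claim would be a reasonable courtesy to the reader.

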### **10.2. DATA MANAGEMENT AND STATISTICAL ANALYSIS**

#### **10.2.1. Statistical analysis plan (SAP)**

The statistical analysis of this study will be performed by the principal investigator at the end of the trial, for all the primary and secondary objectives.

### **10.2.2. Data management**

All CRFs will be reviewed by a health care giver with experience in wound management.

The data will be collected by using a password protected Microsoft Excel database specially prepared for this study. All data not lying within pre-established ranges without explanation from investigators will be queried.

The database will be considered as appropriate for analysis as soon as answers to all queries have been obtained.

### **10.3. GENERAL STATISTICAL CONSIDERATION ON DESCRIPTION OF VARIABLES**

The distribution of parameters will be summarized using descriptive statistics according to characteristics of the study variable:

- Binary, nominal and ordered categorical variables will be summarized by their frequency distribution,
- Continuous variables will be summarized by their number of observations, mean, standard deviation, median, quartiles and range.

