## **1. STUDY DESIGN**

This clinical investigation is an open non-comparative monocenter clinical trial conducted in England. The investigation will be conducted in the Gloucestershire Leg Ulcer Service, at Cheltenham General Hospital and Gloucestershire Royal Hospital (UK).

This clinical trial will include 60 patients; they will be outpatients, community treated, and will be followed for a maximum duration of twelve weeks.

The inclusion period will last a maximum of 12 months.

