### 2.2. SECONDARY OUTCOMES

The secondary criteria are to determine the following:

- Time to reach complete wound closure,
- Relative (and absolute) wound surface area reduction ( $\text{area}_{t0} - \text{area}_{t\text{last}}$ ),
- Percentage of patients with a  $\geq 30\%$  wound area reduction  $[(\text{area}_{t0} - \text{area}_{t\text{last}}) / \text{area}_{t0} \times 100]$  at Week 4 (18,19).
- Evolution of the ankle circumference,
- Patient Quality of Life through a specific the WoundQuol Questionnaire,
- The safety of the tested procedure (compression therapy system and dressings) through the nature and number of emergent local adverse events (i.e., events not present at baseline),
- Patients' acceptability of the procedure, evaluated by the investigator and by the patient,
- The change frequency per week over the treatment period.

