## 5. STUDY CONDUCT

### 5.1. Synoptic diagram of the investigation

For all included patients, the scheduled treatment duration is 12 weeks. Patients will be allocated to the Urgo K2 compression system and a wound dressing from the UrgoStart® range. Both devices must be applied according to manufacturers' recommendations as described in the respective device monographs (Appendix 1&2).

After obtaining the patient's written consent to participate and once all inclusion and exclusion criteria are met, patients will be included in the study. Patients will then be seen at Week 2 and Week 4 ± 3 days during the first month, and then every four weeks, until the 12th week for wound assessment or until complete wound closure if it happens before, with all the visits being documented in the case report form (CRF).

At each of these visits, the investigator will perform a clinical assessment and will measure the wound with a ruler, and will also take a photographic record of the venous leg ulcer.

The treatment may be discontinued, temporarily or definitively, before the required 12 weeks have been completed if the investigator deems this to be necessary: this must be then documented in the Case Report Form (CRF).

A temporary discontinuation of the tested treatment (compression system or the primary dressing) must not exceed 2 weeks; after this time, it will become a permanent discontinuation.

In case of permanent discontinuation, the investigator has to follow-up the patient until Week 12, as expected in the protocol and to treat him at his entire convenience.

The acceptability of the study treatment will also be assessed at each visit planned in the protocol.

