#### **5.4. ASSESSMENT IN THE EVENT OF STUDY WITHDRAWAL BEFORE W12**

A premature study withdrawal may occur for any of the following reasons:

- Withdrawal of informed consent,
- Healing of the tested wound; thus, the patient will have to consult the investigator as soon as possible after the onset of the wound closure to document the event and provide the exact date of the closure,
- Onset of a local adverse event requiring permanent discontinuation of the tested treatment,
- Intercurrent adverse event requiring withdrawal,
- Any other reason, to be documented.

A temporary discontinuation of the study treatment must not exceed two weeks; if it does so, it becomes a permanent discontinuation.

**In case of permanent discontinuation of the treatment (studied compression system or the interactive dressing whatever), the investigator is asked to perform the planned protocol evaluations, at the same frequency, until the final evaluation (Week 12), whatever any local treatment applied.**

On the day of permanent discontinuation, the investigator is asked:

- To make a clinical assessment,
- To measure the study lesion with a ruler,
- To make a photographic record,
- To measure the ankle circumference, in order to follow the evolution of any oedema of the lower limb, if existing.

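### Section 10.3's summary rule for continuous variables does not suit the right-censored time to complete closure; on its natural reading it describes healed ulcers only and gives too short a healing time.

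*Protocol*

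**What the plan says.** Sections 2.2 and 6.2 both put this criterion first among the secondary ones: "Time to reach complete wound closure". Section 1 sets the end of observation: patients "will be followed for a maximum duration of twelve weeks".

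Section 5.4 lists the reasons for leaving before Week 12. One is healing, after which the patient is to be seen promptly to "document the event and provide the exact date of the closure". Another is "Withdrawal of informed consent", and there is an open category for other reasons. Permanently stopping the study treatment does not end observation. Section 5.1 says that "the investigator has to follow-up the patient until Week 12", and section 5.4 repeats the request for the planned evaluations.

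Section 10.3 has two summary rules. Categorical variables get frequency distributions. For the rest: "Continuous variables will be summarized by their number of observations, mean, standard deviation, median, quartiles and range". Section 10.2.1, which carries the statistical analysis plan heading, says who will analyse the primary and secondary objectives (the principal investigator) and names no other method. Section 10.1 rules out statistical tests because the study is non-comparative.

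**The concern.** A time to closure is complete only for an ulcer that closes under observation. For an ulcer still open at Week 12, or open when the patient leaves, all that is known is that the time exceeds the follow-up. A rule built on the mean, SD and quartiles of the recorded values has no place for that information.

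Since closure dates exist only for closed ulcers, the count of observations would naturally be the count of closures, and the mean and median would be conditional on healing within 12 weeks. Such a figure cannot exceed 12 weeks however poorly the treatment performs, and it responds weakly to the closure rate. A reader would take it as the healing time to expect from the treatment.

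**Working it through.** **No figure to reproduce.** The protocol states no healing time, 12-week closure rate, dropout rate or precision. The 60 patients in section 10.1 have no calculation behind them.

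**Inputs.** From the protocol: follow-up of 12 weeks and 60 patients (section 1). Assumed: 12-week closure p from 50% to 90%, a Weibull closure time with shape k, and early loss of 0 to 10%.

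**Formulas.** S(t) = exp(−(Lt)^k), with L = (−ln(1−p))^(1/k) / 12, so that closure by Week 12 equals p.
- All-patient median: (ln 2)^(1/k) / L
- Healed-only median: (−ln(1−p/2))^(1/k) / L
- Restricted mean to 12 weeks, RM: the area under S from 0 to 12, which for k = 1 is p/L
- Healed-only mean: (RM − 12(1−p)) / p

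**Worked case, p = 75%, k = 1.** L = ln 4 / 12 = 0.1155. All-patient median = 0.693 / 0.1155 = 6.0 weeks. Healed-only median = −ln(0.625) / 0.1155 = 0.470 / 0.1155 = 4.07 weeks. RM = 0.75 / 0.1155 = 6.49. Healed-only mean = (6.49 − 3) / 0.75 = 4.66 weeks.

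**Healed-only versus all-patient median (weeks).**

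| 12-week closure | k = 1 (constant hazard) | k = 2 (rising) | k = 3 (steeply rising) |
|---|---|---|---|
| 50% | 4.98 vs 12.00 | 7.73 vs 12.00 | 8.95 vs 12.00 |
| 60% | 4.67 vs 9.08 | 7.49 vs 10.44 | 8.76 vs 10.93 |
| 75% | 4.07 vs 6.00 | 6.99 vs 8.49 | 8.37 vs 9.52 |
| 90% | 3.12 vs 3.61 | 6.11 vs 6.58 | 7.66 vs 8.04 |

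The shortfall is about 3 to 7 weeks at 50% closure, 1.2 to 1.9 at 75% and 0.4 to 0.5 at 90%. For k = 1 the healed-only mean against the restricted mean is 5.31 vs 8.66 at 50%, 4.66 vs 6.49 at 75% and 3.88 vs 4.69 at 90%.

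**Weak response to the closure rate.** For k = 1, moving from 50% to 75% closure halves the all-patient median (12.0 to 6.0) but moves the healed-only median only from 5.0 to 4.1. At 30% closure the all-patient median is not reached by Week 12, yet the healed-only median would still be 5.5 weeks.

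**The other reading: open ulcers given a number.** Averages over 3,000 simulated trials of 60 patients (k = 1, p = 75%, true median 6.0, early loss spread evenly over 12 weeks):

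| Median reported (weeks) | No loss | 10% loss |
|---|---|---|
| Healed only | 4.1 | 3.95 |
| All open ulcers entered at 12 weeks | 6.1 | 6.3 |
| Open ulcers entered at exit time | 6.1 | 5.6 |
| Kaplan-Meier | 5.95 | 6.04 |

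The typical 95% confidence interval for the Kaplan-Meier median is 3.9 to 8.4 weeks, a half-width of (8.4 − 3.9) / 2 = 2.25 weeks. At 60% closure the Kaplan-Meier median is reached in 93 to 95% of simulated trials. At 50% it is reached in only about half (48 to 56%).

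**The case against.** The strongest reply is that section 10.3 is a general paragraph. It does not name time to closure, does not say that only healed patients count, and may be overtaken by a separate analysis plan that is not at hand. That is fair, and the absence of Kaplan-Meier from a protocol would not by itself be a fault. The point here is narrower: a stated rule, with no exception, does not fit a stated criterion. If a separate plan deals with it, a cross-reference in 10.3 settles the matter.

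A second reply is that open ulcers could be entered at 12 weeks. The median is then nearly right when more than half close and few are lost. This stands for the median, but the protocol does not say to do it, and the mean would be only a 12-week restricted mean.

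A third is that the size is assumed. This also stands. The only closure figure in the document, 30–75% in the Introduction, is for six months and for venous leg ulcers in general, whereas the trial takes ulcers under six weeks old. Carried back at constant hazard, 1 − 0.70^(12/26) and 1 − 0.25^(12/26) give about 15% to 47% at 12 weeks. In that range the all-patient median is not reached, so the healed-only figure would mislead more.

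Finally, precision is limited. Scheduled visits are at Weeks 2, 4, 8 and 12, and the bandage may stay on for up to 7 days (Appendix (i)), so differences of a few tenths of a week mean little. At 75% closure the 1.9-week bias is slightly smaller than the 2.25-week half-width of the confidence interval. It is nevertheless systematic, and more patients would not reduce it.

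**Conclusion.** The point holds. No reading of the rule makes all of its summaries valid for this criterion, and the natural reading makes the healing time too short at every closure rate and hazard shape tried. The bias is large if about half the ulcers close and small if about nine in ten do. These sizes rest on assumed closure rates and hazard shapes and on exactly known closure dates. The direction does not depend on the assumed rate or shape.

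The consequence is limited to one descriptive secondary criterion. The main criterion in section 6.1, the proportion closed at the last available visit, is unaffected, and printing the number of observations would show how many ulcers the summary covers. It should be corrected before analysis but does not threaten the main result. Confidence is medium, because section 10.3 does not expressly assign this criterion to the rule.

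**What to change.** Add a paragraph to section 10.3 along these lines:

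> Time to complete closure is estimated by Kaplan-Meier in the ITT population. Closure is the event, including when it ends participation early under section 5.4. Unclosed ulcers are censored at the last documented assessment, Week 12 at the latest. The median is reported with a 95% confidence interval, or as not reached, together with cumulative closure at Week 12. Any mean or median among healed patients is labelled as conditional on healing within 12 weeks.

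Stating that closure is an event matters because section 5.4 lists healing among the premature withdrawals. Patients who stop treatment but remain under evaluation should not be censored at that point, in line with sections 5.1 and 5.4.

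The cost is one paragraph and a standard estimate from data already collected. It is estimation, so it is compatible with the no-tests statement in section 10.1. The drawbacks are slightly more analysis work, a less favourable-looking healing time and, if only about half the ulcers close, a median that may have to be reported as not reached.
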